### **6.3 Exclusion Criteria**

1. Subjects with active medical problems
2. Subjects on chronic prescription or OTC medication that cannot be stopped 2 weeks prior to and during the study.
3. Subjects incapable of multiple blood draws (HCT < 30mg/dL)
4. Subjects with a history of rhabdomyolysis
5. Subjects with a history of drug-related myalgias
6. Subjects with a history or diagnosis of hemorrhagic tendencies or blood dyscrasias
7. Subjects with a history of GI bleed or peptic ulcer disease
8. Subjects who smoke tobacco or have ongoing alcohol or illegal drug use
9. Subjects who are pregnant, lactating, or trying to conceive during the study period
10. Subjects allergic to fluvastatin or rifampin or any known component of the medications
11. Anyone who in the opinion of the study investigators is unable to do the study

## **7 CONCURRENT MEDICATIONS**

All subjects should not take any other concurrent medication

### **7.1 Allowed Medications and Treatments**

Subjects will take no other medications two weeks prior to the study and during the time course of the study including prescription medications, over-the-counter medications, dietary supplements, or drugs of abuse.

### **7.2 Prohibited Medications and Treatments**

No other medications besides study medications are allowed.

## **8 STUDY TREATMENTS**

### **8.1 Method of Assigning Subjects to Treatment Groups.**

Once included in the study, patients will be randomized using computer-generated random numbers, corresponding to each treatment. This will be performed by someone other than the investigator and will ensure equal number of patients in each treatment sequence.

## 8.2 Blinding

The study is not blinded

## 8.3 Formulation of Test and Control Products

### 8.3.1 Formulation of Test and Control Product

Fluvastatin capsule, developed by Novartis Pharmaceutical Corporation, is an HMG-CoA reductase inhibitor to reduce elevated TC, LDL-C, Apo B, and TG, and to increase HDL-C in adult patients with hypercholesterolemia. Fluvastatin sodium is a white to pale yellow, hygroscopic powder soluble in water, ethanol and methanol. LESCOL is supplied as capsules containing fluvastatin sodium, equivalent to 20 mg or 40 mg of fluvastatin.

Trade Drug Name	Lescol
Generic Drug name	Fluvastatin sodium (capsules)
Investigational Drug Name	
Identify the name of the manufacturer or source of investigational drug/biologic:	Novartis Pharmaceuticals Corporation
Active ingredient	fluvastatin sodium
Inactive ingredient	calcium carbonate, gelatin, magnesium stearate, microcrystalline cellulose, pregelatinized starch (corn), red iron oxide, sodium bicarbonate, talc, titanium dioxide, yellow iron oxide, and other ingredients.
PH	4.5

Rifampin is used only to treat or prevent infections that are proven or strongly suspected to be caused by bacteria. Rifampin is a red-brown crystalline powder very slightly soluble in water at neutral pH, freely soluble in chloroform, soluble in ethyl acetate and in methanol.

Trade Drug Name:	RIFADIN IV
Generic Drug Name:	RIFAMPIN

Identify the name of the manufacturer or source of investigational drug/biologic:	Sanofi-Aventis
Active Ingredient	rifampin 600 mg
Inactivate Ingredient	sodium formaldehyde sulfoxylate 10 mg, and sodium hydroxide to adjust pH
PH	7.8–8.8

## 8.4 Supply of Study Medications at the Site

The investigator will supply study drug to the investigational sites.

### Dosage/Dosage Regimen

fluvastatin 20 mg by mouth as a 20 mg Lescol® capsule

30-min intravenous infusion of rifampin (Rifadin®, Sanofi-Aventis, Bridgewater, NJ) 600 mg in 10 ml sterile normal saline

### Dispensing

The investigator has authority to dispense the drug

#### 8.4.1 Administration Instructions

During study period 1 or 2, subjects will take fluvastatin 20 mg by mouth as a 20mg lescol capsule. Subjects will also receive 30-min intravenous infusion of rifampin (Rifadin®, Sanofi-Aventis, Bridgewater, NJ) 600 mg in 10 ml sterile normal saline at a rate of 20 mg/min immediately prior to fluvastatin dosing on one of the study periods. All subjects will be asked to abstain from caffeinated beverages, alcoholic beverages, all fruit juices, oranges, and grapefruits from 7am the day before each study period until the study is complete.

### Storage

Study drugs should be stored by the study site at controlled room temperature, 15 to 30°C (59 to 86°F). If the temperature of study drug storage in the clinic/pharmacy exceeds or falls below this range, this should be reported to the Sponsor or designee and captured as a deviation. It is important store the medication in original packaging (foil pouch and protected from light) at room temperature according to the instructions outlined on the Drug Administration Instructions.

## **8.5 Study Drug Accountability**

An accurate and current accounting of the dispensing and return of study drug for each subject will be maintained on an ongoing basis by a member of the study site staff. The number of study drug dispensed and returned by the subject will be recorded on the Investigational Drug Accountability Record. The study monitor will verify these documents throughout the course of the study.

## **8.6 Measures of Treatment Compliance**

Investigator will monitor the subjects when they take fluvastatin and when they undergo 30-min intravenous infusion of rifampin (Rifadin®; Sanofi-Aventis, Bridgewater, NJ) 600 mg in 10 ml sterile normal saline at a rate of 20 mg/min

# **9 STUDY PROCEDURES AND GUIDELINES**

A Schedule of Events representing the required testing procedures to be performed for the duration of the study is diagrammed in Appendix 1.

Prior to conducting any study-related activities, written informed consent and the Health Insurance Portability and Accountability Act (HIPAA) authorization must be signed and dated by the subject. If appropriate, assent must also be obtained prior to conducting any study-related activities.

### **9.1 Clinical Assessments**

#### **9.1.1 Concomitant Medications**

Only subjects who take no other medications two weeks prior to the study and during the time course of the study including prescription medications, over-the-counter medications, dietary supplements, or drugs of abuse will be allowed to participate in the trial.

#### **9.1.2 Demographics**

A descriptive analysis of the demographic characteristics of the study subjects will be performed. Demographic characteristics of interest are age, race, height, weight and gender will be recorded at screening.

#### **9.1.3 Medical History**

Relevant medical history, including history of current disease, other pertinent respiratory history, and information regarding underlying diseases will be recorded at screening

#### **9.1.4 Physical Examination**

A complete physical examination will be performed by either the investigator who is a physician at screening visit. Qualified staff (MD) may complete the abbreviated physical exam at all other visits. New abnormal physical exam findings must be documented and will be followed by a physician or other qualified staff at the next scheduled visit.

### **9.1.5 Vital Signs**

Body temperature, blood pressure, pulse and respirations will be performed after resting for 5 minutes at the screening

### **9.1.6 Adverse Events**

Information regarding occurrence of adverse events will be captured throughout the study. Duration (start and stop dates and times), severity/grade, outcome, treatment and relation to study drug will be recorded on the case report form (CRF).

## **9.2 Clinical Laboratory Measurements**

### **9.2.1 Hematology**

Blood will be obtained and sent to the site's clinical hematology lab for a complete blood count (hemoglobin, hematocrit, red blood cell count, white blood cell count, white blood cell differential, and platelet count), erythrocyte sedimentation rate (ESR), and serum C-reactive protein (CRP) determinations for assessment of systemic evidence for infection and/or inflammation.

### **9.2.2 Blood Chemistry Profile**

Blood will be obtained and sent to each site's clinical chemistry lab for Hgb, HCT, RBC, Plt, WBC with differential, Ca++, Na+, K+, Cl-, CO2, glucose, serum creatinine, BUN, phosphorus, AST, ALT, alkaline phosphatase, CPK, total bilirubin, albumin, total protein, cholesterol, and triglycerides.

### **9.2.3 Pregnancy Test**

A urine or serum pregnancy test will be obtained from female subjects who are of childbearing age prior to their participation in the study.

### **9.2.4 Urinalysis**

Urine will be obtained and sent to each site's clinical laboratory for determination of (list as applicable) color, specific gravity, pH, protein, glucose, ketones, and blood.

## **9.3 Pharmacokinetic Measurements**

Blood for determination of serum concentrations of fluvastatin will be collected 0, 0.33, 0.67, 1, 1.5, 2, 2.5, 3, 4, 6, 9, and 12h after fluvastatin dosing. Plasma will be separated and stored at -80°C until analysis of drug levels.

Plasma concentrations of fluvastatin and rifampin in all collected plasma samples will be measured via a previously validated tandem liquid chromatography mass spectrometry (LC-MS/MS) method. Determined plasma concentrations of fluvastatin will then be modeled using pharmacokinetic modeling software to calculate the corresponding AUC, oral clearance, and oral volume of distribution of fluvastatin in the treatment groups.

## **9.4 Research Laboratory Measurements**

Cell Count and Differential blood sample (30mL) for determination of Hgb, HCT, RBC, Plt, WBC with differential will be collected during screen.

## 10 EVALUATIONS BY VISIT

### 10.1 Screening Visit ( at least one week prior to study period 1)

- 1) Written informed consent will be obtained.
- 2) A medical history and a physical exam including vital signs (oral temperature, heart rate, blood pressure, and respiratory rate), height, and weight will be performed. Subjects will also be asked about prescriptions, dietary supplements, and illegal drug use.
- 3) Blood (30 ml) and urine tests (Hgb, HCT, RBC, Plt, WBC with differential, Ca++, Na+, K+, Cl-, CO2, glucose, serum creatinine, BUN, phosphorus, AST, ALT, alkaline phosphatase, CPK, total bilirubin, albumin, total protein, cholesterol, triglycerides, urinalysis).
- 4) For female subjects, a urine pregnancy test will be required.

### 10.2 Study period 1 (Tuesday of the Week):

- 1) **Admit to Clinical Research Center (CRC) at UCSF** - subjects will be admitted to the Clinical Research Center (CRC) at UCSF (12th Floor Moffitt Hospital). Subjects will be discharged after the 12 hour blood sample.
- 2) **Urine Pregnancy Test** - For female subjects, a urine pregnancy test will be performed.
- 3) **Catheter placement**- For the purpose of administering rifampin and drawing blood samples, two indwelling peripheral venous catheters will be inserted aseptically into the forearm vein by a nurse in the CRC immediately prior to medication administration. The rifampin catheter will be removed immediately after rifampin administration, the second catheter will be removed after the final blood draw. If the catheter malfunctions and needs to be removed prior to the last blood draw, a subject may choose to have remaining blood draws via peripheral venous needle sticks or have a new catheter placed.
- 4) **Dose study medications**: Subjects will receive one of the following dose of medications:
  - a. Dose fluvastatin 20 mg by mouth as a 20 mg Lescol® capsule (t = 0)
  - b. Dose rifampin 600mg IV infusion over 30 minutes (t = -30 minutes) followed by a dose of fluvastatin 20 mg by mouth as a 20 mg Lescol® capsule (t = 0)The order in which subjects receive the above treatments will be randomized via random number generator.

**5) Serial blood sampling-** Venous blood samples (8 mL) will be drawn at 0, 0.33, 0.67, 1, 1.5, 2, 2.5, 3, 4, 6, 9, and 12h after fluvastatin dosing. Plasma will be separated and stored at -80°C until analysis of drug levels.

### **10.3 Study Period 2 (Thursday of the week )**

- 1) Admit to Clinical Research Center (CRC) at UCSF** - During each study period, subjects will be admitted to the Clinical Research Center (CRC) at UCSF (12th Floor Moffitt Hospital). Subjects will be discharged after the 12 hour blood sample.
- 2) Urine Pregnancy Test** - For female subjects, a urine pregnancy test will be performed.
- 3) Catheter placement-** For the purpose of administering rifampin and drawing blood samples, two indwelling peripheral venous catheter will be inserted aseptically into the forearm vein by a nurse in the CRC immediately prior to medication administration. The rifampin catheter will be removed immediately after rifampin administration, the second catheter will be removed after the final blood draw. If the catheter malfunctions and needs to be removed prior to the last blood draw, a subject may choose to have remaining blood draws via peripheral venous needle sticks or have a new catheter placed.
- 4) Dose study medications:** Subjects will receive one of the following dose of medications:
  - a. Dose fluvastatin 20 mg by mouth as a 20 mg Lescol® capsule (t = 0)
  - b. Dose rifampin 600mg IV infusion over 30 minutes (t = -30 minutes) followed by a dose of fluvastatin 20 mg by mouth as a 20 mg Lescol® capsule (t = 0)The order in which subjects receive the above treatments will be randomized via random number generator.
- 5) Serial blood sampling-** Venous blood samples (8 mL) will be drawn at 0, 0.33, 0.67, 1, 1.5, 2, 2.5, 3, 4, 6, 9 and 12h after fluvastatin dosing. Plasma will be separated and stored at -80°C until analysis of drug levels.

**6) Safety Monitoring-** At study completion, subjects will have repeat physical examination and repeat hematology, chemistries, liver, renal and coagulation laboratories for safety monitoring.

## **11 ADVERSE EXPERIENCE REPORTING AND DOCUMENTATION**

### **11.1 Adverse Events**

An adverse event (AE) is any untoward medical occurrence in a clinical investigation of a patient administered a pharmaceutical product and that does not necessarily have a causal

relationship with the treatment. An AE is therefore any unfavorable and unintended sign (including an abnormal laboratory finding), symptom or disease temporally associated with the administration of an investigational product, whether or not related to that investigational product. An unexpected AE is one of a type not identified in nature, severity, or frequency in the current Investigator's Brochure or of greater severity or frequency than expected based on the information in the Investigator's Brochure.

The Investigator will probe, via discussion with the subject, for the occurrence of AEs during each subject visit and record the information in the site's source documents.

Adverse events will be recorded in the patient CRF. Adverse events will be described by duration (start and stop dates and times), severity, outcome, treatment and relation to study drug, or if unrelated, the cause.

### **AE Severity**

The National Cancer Institute's Common Terminology Criteria for Adverse Events (CTCAE) Version 3.0 should be used to assess and grade AE severity, including laboratory abnormalities judged to be clinically significant. The modified criteria can be found in the study manual. If the experience is not covered in the modified criteria, the guidelines shown in Table 1 below should be used to grade severity. It should be pointed out that the term "severe" is a measure of intensity and that a severe AE is not necessarily serious.

**Table 1. AE Severity Grading**

Severity (Toxicity Grade)	Description
Mild (1)	Transient or mild discomfort; no limitation in activity; no medical intervention or therapy required. The subject may be aware of the sign or symptom but tolerates it reasonably well.
Moderate (2)	Mild to moderate limitation in activity, no or minimal medical intervention/therapy required.
Severe (3)	Marked limitation in activity, medical intervention/therapy required, hospitalizations possible.
Life-threatening (4)	The subject is at risk of death due to the adverse experience as it occurred. This does not refer to an experience that hypothetically might have caused death if it were more severe.

### **AE Relationship to Study Drug**

The relationship of an AE to the study drug should be assessed using the following the guidelines in Table 2.

**Table 2. AE Relationship to Study Drug**

Relationship to Drug	Comment

Definitely	Previously known toxicity of agent; or an event that follows a reasonable temporal sequence from administration of the drug; that follows a known or expected response pattern to the suspected drug; that is confirmed by stopping or reducing the dosage of the drug; and that is not explained by any other reasonable hypothesis.
Probably	An event that follows a reasonable temporal sequence from administration of the drug; that follows a known or expected response pattern to the suspected drug; that is confirmed by stopping or reducing the dosage of the drug; and that is unlikely to be explained by the known characteristics of the subject's clinical state or by other interventions.
Possibly	An event that follows a reasonable temporal sequence from administration of the drug; that follows a known or expected response pattern to that suspected drug; but that could readily have been produced by a number of other factors.
Unrelated	An event that can be determined with certainty to have no relationship to the study drug.

## 11.2 Serious Adverse Experiences (SAE)

An SAE is defined as any AE occurring at any dose that results in any of the following outcomes:

- death
- a life-threatening adverse experience
- inpatient hospitalization or prolongation of existing hospitalization
- a persistent or significant disability/incapacity
- a congenital anomaly/birth defect
- Other important medical events may also be considered an SAE when, based on appropriate medical judgment, they jeopardize the subject or require intervention to prevent one of the outcomes listed.

### 11.2.1 Serious Adverse Experience Reporting

Study sites will document all SAEs that occur (whether or not related to study drug) per [UCSF CHR Guidelines](#). The collection period for all SAEs will begin after informed consent is obtained and end after procedures for the final study visit have been completed.

In accordance with the standard operating procedures and policies of the local Institutional Review Board (IRB)/Independent Ethics Committee (IEC), the site investigator will report SAEs to the IRB/IEC.

## **12 DISCONTINUATION AND REPLACEMENT OF SUBJECTS**

### **12.1 Early Discontinuation of Study Drug**

A subject may be discontinued from study treatment at any time if the subject, the investigator, or the Sponsor feels that it is not in the subject's best interest to continue. The following is a list of possible reasons for study treatment discontinuation:

- Subject withdrawal of consent (or assent)
- Subject is not compliant with study procedures
- Adverse event that in the opinion of the investigator would be in the best interest of the subject to discontinue study treatment
- Protocol violation requiring discontinuation of study treatment
- Lost to follow-up
- Sponsor request for early termination of study
- Positive pregnancy test (females)

If a subject is withdrawn from treatment due to an adverse event, the subject will be followed and treated by the Investigator until the abnormal parameter or symptom has resolved or stabilized.

All subjects who discontinue study treatment should come in for an early discontinuation visit as soon as possible and then should be encouraged to complete all remaining scheduled visits and procedures.

All subjects are free to withdraw from participation at any time, for any reason, specified or unspecified, and without prejudice.

Reasonable attempts will be made by the investigator to provide a reason for subject withdrawals. The reason for the subject's withdrawal from the study will be specified in the subject's source documents. Refer to Section 10 for early termination procedures.

### **12.2 Withdrawal of Subjects from the Study**

A subject may be withdrawn from the study at any time if the subject, the investigator, or the Sponsor feels that it is not in the subject's best interest to continue.

All subjects are free to withdraw from participation at any time, for any reason, specified or unspecified, and without prejudice.

Reasonable attempts will be made by the investigator to provide a reason for subject withdrawals. The reason for the subject's withdrawal from the study will be specified in the subject's source documents. Subjects who withdraw after study period 1 but prior to study period 2 should be encouraged to come in for a final visit (and the procedures to be followed would include those for their next scheduled visit).

### **12.3 Replacement of Subjects**

Subjects who withdraw from the study treatment will be replaced.

Subjects who withdraw from the study will be replaced.

## **13 PROTOCOL VIOLATIONS**

A protocol violation occurs when the subject, investigator, or sponsor fails to adhere to significant protocol requirements affecting the inclusion, exclusion, subject safety and primary endpoint criteria. Protocol violations for this study include, but are not limited to, the following:

- Failure to meet inclusion/exclusion criteria
- Use of a concomitant medication

Failure to comply with Good Clinical Practice (GCP) guidelines will also result in a protocol violation. The sponsor will determine if a protocol violation will result in withdrawal of a subject.

When a protocol violation occurs, it will be discussed with the investigator and a Protocol Violation Form detailing the violation will be generated. This form will be signed by a Sponsor representative and the Investigator. A copy of the form will be filed in the site's regulatory binder and in the Sponsor's files.

## **14 DATA SAFETY MONITORING**

The study does not required a Data and Safety Monitoring Board

## **15 STATISTICAL METHODS AND CONSIDERATIONS**

Prior to the analysis of the final study data, a detailed Statistical Analysis Plan (SAP) will be written describing all analyses that will be performed. The SAP will contain any modifications to the analysis plan described below.

### **15.1 Data Sets Analyzed**

All eligible patients who are randomized into the study will be included in the data analysis.

### **15.2 Demographic and Baseline Characteristics**

A descriptive analysis of the demographic characteristics of the study subjects will be performed. Demographic characteristics of interest are age, race, height, weight and gender.

### **15.3 Analysis of Primary Endpoint**

AUC0-∞ will be calculated using the trapezoidal rule from time 0 to Clast + Clast/ke. Parameters such as maximum plasma concentration (Cmax) and time to Cmax (Tmax) will be determined from the observed data. The terminal elimination rate constant (ke) will be obtained using linear regression of log transformed concentrations over the terminal log-linear decline phase. Oral clearance (CL/F) will be calculated using Dose/AUC0-∞. Other estimated pharmacokinetic parameters will be calculated using non-

compartmental methods with WinNonlin Professional software (Pharsight, Inc., Mountain View, CA). Log-transformed pharmacokinetic parameters will be compared across treatments with analysis of variance for repeated measures. Differences will be regarded as statistically significant if  $p < 0.05$ . Data will be presented as mean values with standard deviations. Each subject will serve as his/her own control. Differences in pharmacokinetic parameters between treatments will be calculated using student's paired t-test. Statistical calculations will be done using STATA 10.0 (StataCorporation, College Station, TX).

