## 4 STUDY DESIGN

### 4.1 Study Overview

The effect of rifampin on the pharmacokinetics of fluvastatin will be studied in healthy volunteers in a two-period, randomized, unblinded, crossover clinical trial. On period 1 of the study, subjects will be randomized to one of two treatment groups:

- (i) one oral dose of fluvastatin (Lescol®) 20mg capsule
- (ii) one oral dose of fluvastatin (Lescol®) 20mg capsule immediately following a 30-min intravenous infusion of rifampin 600mg in 10ml Normal Saline.

The two study periods will preferentially be on a Tuesday and Thursday, separated by one day of washout. Subjects will be instructed to fast overnight the day before study periods 1 and 2, and for 3h post-dosing. In both treatments, venous blood samples (~8ml each) will be drawn at 0, 0.33, 0.67, 1, 1.5, 2, 2.5, 3, 4, 6, 9, 12h after fluvastatin dosing. Period 2 will begin after at least a 1-day washout when subjects will receive the second treatment, followed by blood draws at the same time points as after fluvastatin dosing alone.

	Period 1	Period 2
Group 1	A	B
Group 2	B	A

A= fluvastatin; B =rifampin +fluvastatin

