### **5.2 Secondary Efficacy Endpoints**

Secondary outcomes will include fluvastatin maximum plasma concentration (Cmax) and time to Cmax (Tmax)

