#### **15.4 Analysis of Secondary Endpoints**

Parameters such as maximum plasma concentration (Cmax) and time to Cmax (Tmax) will be determined from the observed data. The terminal elimination rate constant (ke) will be obtained using linear regression of log transformed concentrations over the terminal log-linear decline phase. Oral clearance (CL/F) will be calculated using Dose/AUC $0-\infty$ .

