#### **15.6 Sample Size and Randomization**

Using a paired t-test and prior data, a sample size of n=10 in each group is needed to detect a 50% difference in AUC $0-12$  between the two study regimens with a statistical power of 80% (two sided alpha = 0.05) and standard deviation of 50%. Due to the lesser effects of rifampin on fluvastatin AUC, the within subject variability can affect the sample size. We plan to enroll sample size of 12 subjects to maintain an adequate sample size in case of potential attrition.

Once included in the study, patients will be randomized using computer-generated random numbers, corresponding to each treatment. This will be performed by someone other than the investigator and will ensure equal number of patients in each treatment sequence.

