## 15.3 Analysis of Primary Endpoint

AUC0-∞ will be calculated using the trapezoidal rule from time 0 to Clast + Clast/ke. Log-transformed pharmacokinetic parameters will be compared across treatments with analysis of variance for repeated measures. Differences will be regarded as statistically significant if p< 0.05. Data will be presented as mean values with standard deviations. Each subject will serve as his/her own control. Differences in pharmacokinetic parameters between treatments will be calculated using student's paired t-test. Statistical calculations will be done using STATA 10.0 (StataCorporation, College Station, TX).

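### Tmax falls under the general mean ± SD and paired t-test rule, where one late peak among 10-12 subjects can erase a real shift; a median and Hodges-Lehmann summary would be more robust

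*Combined protocol and SAP*

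**What the plan says.** The combined file holds two protocols, one for single-dose rifampin and one for the enzyme-induced state. The rules on this point are nearly the same in both.

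- **Status of Tmax.** Section 5.2: "Secondary outcomes will include fluvastatin maximum plasma concentration (Cmax) and time to Cmax (Tmax".
- **How it is obtained.** Section 15.4: "time to Cmax (Tmax) will be determined from the observed data". Sections 4.1 and 9.3 fix the possible values, since blood is drawn at "0, 0.33, 0.67, 1, 1.5, 2, 2.5, 3, 4, 6, 9, and 12h after fluvastatin dosing".
- **Analysis rule.** Section 15.3 says "Log-transformed pharmacokinetic parameters will be compared across treatments with analysis of variance for repeated measures" and also "Differences in pharmacokinetic parameters between treatments will be calculated using student's paired t-test".
- **Summary rule.** Section 15.3: "Data will be presented as mean values with standard deviations".
- **Tmax-specific rule.** There is none. Section 15.4 of both protocols says how Tmax is obtained and names no test or summary. No median, range or rank method appears anywhere in either protocol.

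In the single-dose protocol, 15.3 lists Cmax and Tmax among the parameters before stating the tests. In the induced-state protocol, 15.3 does not list them, but the synopsis does and then applies the same rules.

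**The concern.** Sampling gaps are 0.33 to 0.5 h up to 3 h, then 1, 2, 3 and 3 h. A profile that peaks late therefore moves Tmax by hours, while the shift of interest is likely to be one early slot. With 10-12 subjects, one such profile can dominate the mean difference and inflate the SD in both the summary table and the paired t-test. A real delay in absorption could then be reported as no change, or with the wrong sign. At stake is the description of one secondary outcome.

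**Working it through.** **1. The plan's own figure.** Section 15.6 states n=10 for a 50% difference in AUC0-12 with SD 50%, 80% power and "two sided alpha = 0.05". If 50% is read as the SD of the within-subject difference, d = 50/50 = 1.0. Paired-t power is P(|T| > t(0.975, n-1)), with T noncentral t on n-1 df and noncentrality d√n. The results are 0.748 at n=9, 0.803 at n=10 and 0.883 at n=12, so n=10 reproduces. The figure concerns AUC0-12; the documents give no effect, SD or sample size for Tmax.

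**2. A constructed example on the protocol's grid (n=12).** The data are invented to show the mechanism. Seven subjects go from 0.67 h (control) to 1 h (rifampin), a difference of 0.33 h. Five go from 1 h to 1.5 h, a difference of 0.50 h.

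- No late peak: mean difference = (7×0.33 + 5×0.50)/12 = 4.81/12 = +0.40 h.
- One 0.67 h control profile moved to 6 h: its difference becomes 1 - 6 = -5 h, and the mean is (4.81 - 0.33 - 5)/12 = -0.52/12 = -0.04 h.
- Two such profiles: (4.81 - 2×0.33 - 2×5)/12 = -5.85/12 = -0.49 h.

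The log t-test below is the two-treatment repeated-measures ANOVA on log Tmax without a period term. The Hodges-Lehmann (HL) estimate is the median of all pairwise averages of the 12 differences. The signed-rank test is exact.

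| Late control profiles | Control mean ± SD (h) | Mean diff (h) | Paired t p | Log t p | Median diff (h) | HL (h) | Signed-rank p |
|---|---|---|---|---|---|---|---|
| 0 | 0.81 ± 0.17 | +0.40 | <0.001 | <0.001 | 0.33 | 0.42 | <0.001 |
| 1 | 1.25 ± 1.50 | -0.04 | 0.93 | 0.25 | 0.33 | 0.42 | 0.023 |
| 2 | 1.70 ± 2.02 | -0.49 | 0.44 | 0.88 | 0.33 | 0.42 | 0.23 |

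The median and HL differences do not move. The signed-rank p-value does: with two late profiles it is no longer significant either.

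**3. Simulation on the grid (n=12, 2000 replicates).** All distributional inputs are assumptions: log-normal Tmax with median 0.8 h and log SD 0.3, late peaks uniform on 2.5-6 h, a true shift of 0.33 h, values snapped to the nearest sampling time, and the two periods independent. The signed-rank test is exact, allows for ties and drops zero differences.

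| Late-peak rate | Raw paired t | Log t | Exact signed-rank |
|---|---|---|---|
| 0% | 74% | 78% | 62% |
| 10% | 17% | 31% | 26% |
| 20% | 8% | 17% | 12% |

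The Monte Carlo standard error of the 26% is √(0.26×0.74/2000), about 1 point. At 10% late peaks the SD of the estimate is about 0.45 h for the mean difference and 0.25 h for HL. At 20% the advantage narrows to about 0.60 h against 0.46 h.

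**4. A second simulation model.** Here Tmax is drawn directly on the grid, the true delay is one slot, late peaks fall at 4 or 6 h, and there are 4000 trials. At 0 / 5 / 10 / 15% late peaks, power is 0.93 / 0.41 / 0.22 / 0.14 for the raw paired t, 0.92 / 0.56 / 0.37 / 0.27 for the log t, and 0.87 / 0.53 / 0.35 / 0.25 for the exact signed-rank. With no true shift, rejection rates are 0.018-0.045, 0.040-0.046 and 0.023-0.035 respectively, so none exceeds 0.05.

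**The case against.** Four objections carry weight.

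- **The text is less definite than it could be.** Neither test sentence names Tmax, and 15.3 of the induced-state protocol does not list it. Section 15 of both protocols also promises a detailed SAP with any modifications before final analysis. This stands as a caution about wording. But if the general rule does not cover Tmax, a named secondary outcome has no analysis, and the same sentence is needed in 15.4.
- **The late-peak rate is assumed.** No section gives a Tmax distribution. Section 4.1 requires an overnight fast and 3 h of fasting after dosing, which limits food as a cause of late peaks. If late peaks do not occur, the mean-based summary does little harm.
- **The suggested test has a power cost.** With no late peaks, exact signed-rank power is 62% against 78% for the log t-test, a loss of 16 points. Ties and zero differences are common on this grid.
- **The stakes are low.** No power claim or decision rule rests on Tmax.

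A reader might also infer that the log ANOVA is unsuitable because the sampling times are unevenly spaced in log time. The documents do not support that. Log steps run from ln(3/2.5) = 0.18 to ln(0.67/0.33) = 0.71, a ratio of 3.9. Raw steps run from 0.33 to 3 h, a ratio of about 9. A signed-rank test on raw differences depends on the grid too, and the log t-test had higher power than the exact signed-rank test at every late-peak rate simulated.

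**Conclusion.** The point holds as a low-severity improvement to how Tmax is summarised and estimated. The weak parts are the mean ± SD and the raw paired t-test. One late control profile in 12 takes the constructed mean difference from +0.40 h to -0.04 h, while HL stays at 0.42 h. With 10% late peaks the mean difference is nearly twice as variable as HL (about 0.45 h against 0.25 h). The size rests on the assumed Tmax distribution and late-peak rate; the direction follows from the grid and the small sample.

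Two stronger conclusions might be inferred and should not be. The first is that the plan risks false positives on Tmax: simulated rejection rates under no shift stayed at or below 0.046. The second is that a rank test would recover power relative to the log analysis: it has less, 26% against 31% at 10% late peaks. The AUC conclusions and n=10 are untouched.

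**What to change.** In 15.4 of both protocols, exempt Tmax from the mean ± SD and raw paired t-test rule. State that Tmax will be reported as median and range by treatment, and that the treatment difference will be the Hodges-Lehmann estimate on untransformed times with a 95% CI from a signed-rank analysis, or from its two-period version that allows for sequence. Say that the test is exact and how ties and zero differences are handled.

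The cost is one sentence per protocol, with no change to sampling, sample size or the AUC analysis. The signed-rank test gives up power against the log t-test, so the sentence should be justified by the robust estimate. If the team keeps the log analysis of Tmax as well, it should say beforehand which test is the main one.
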